## 2.2 Data and Safety Monitoring Board

The DSMB is responsible for safeguarding the interests of study participants, assessing the safety and efficacy of study procedures, and for monitoring the overall conduct of the study. The recommendations will be forwarded to the Executive Committee and the sponsor for final decision.

The DSMB is an independent group advisory to the executive board and is required to provide recommendations about continuing, and stopping the study. In addition, the DSMB is asked to make recommendations, as appropriate, about the benefit/risk ratio of procedures and participant burden

The DSMB will convene annually and at the milestones of 40 and 80 patients enrolled as well as at study conclusion to review safety data.

Notification of and referral for abnormal findings Data will be collected by the research team. Study data will be entered into the data collection forms or recorded electronically as they are collected during the study visit. The PIs will monitor all data for any inconsistencies or irregularity. If unanticipated adverse events or SAE of importance (symptomatic hemorrhagic transformation) are observed, they will be reported to the DSMB within 24 hours. All other AE's will be reported during scheduled meetings and to the IRB according to standard AE reporting policies. The Principal Investigator will forward all decisions to the regulatory authority as appropriate.

## 2.3 Stroke Adjudication Committee (SACCO)

The Stroke Adjudication Committee will review and adjudicate all stroke endpoints. The committee will not be blinded to patient and study medication arm during the review of each stroke endpoint case.

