### 1.3 Name and Description of Investigational Product or Description of Intervention

Apixaban, a factor Xa (FXa) inhibitor, is chemically described as 1-(4-methoxyphenyl)-7-oxo-6-[4-(2-oxopiperidin-1-yl)phenyl]-4,5,6,7-tetrahydro-1H-pyrazolo[3,4-c]pyridine-3-carboxamide. Its molecular formula is C25H25N5O4, which corresponds to a molecular weight of 459.5. Apixaban has the following structural formula:

Apixaban is a white to pale-yellow powder. At physiological pH (1.2–6.8), apixaban does not ionize; its aqueous solubility across the physiological pH range is ~0.04 mg/mL.

This study is an open label, randomized, active controlled pilot study of Apixaban in subjects with NVAf who have, within 48 hours from signs and symptoms, been diagnosed with a TIA or a Small to Medium Ischemic Stroke as defined by the SACCO (see section 2.3).

In this study 120 patients with NVAf who have had a recent small or medium stroke or TIA (within 0-48 hours) will receive Apixaban twice a day for 180 days with drug initiation day 0-3 (TIA), day 3-5 (small stroke) or day 7-9 (medium stroke) respectively or receive standard of care warfarin starting at day 7±5 (TIA) or day 14 ±5 (small to medium ischemic stroke).

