#### 4 INVESTIGATIONAL PLAN

##### 4.1 General Schema of Study Design

This will be a multi-center, open label, randomized, active control, parallel-group pilot trial to examine the effect of initiation of APIXABAN at days 0-3 (TIA), days 3-5 (small stroke) and days 7-9 (medium stroke) to decrease fatal and/or recurrent stroke/TIA in 120 subjects who have suffered a recent (0 to 48 hours from symptoms) TIA, or small to medium ischemic stroke as defined by appendix 13.1 compared to standard of care warfarin treatment regimen. Subjects will be randomly assigned in a 1:1 ratio to one of two treatment arms (apixaban or warfarin). Subjects will be followed for a total of 180 days from screening through follow-up.

[figure not shown]

Figure 1

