**5.2 Baseline Visit/Randomization**

The baseline/randomization visit will be performed up to 48 hours after signs and symptoms of stroke or TIA, and will be combined with the screening visit as long as all inclusion/exclusion criteria have met prior to randomization.

After subjects have been screened and enrolled in the study, baseline assessments will be performed. Patients will be stratified according to their type of stroke ( TIA, small or medium stroke) and randomized 1:1 in each group to ensure for equal number of subjects for each three types. Treatment with APIXABAN 5mg or 2.5mg based on clinical characteristics defined in section 1.4 or Warfarin ( target INR 2-3) will begin based on the randomization treatment regimen. Study treatment regimen is initiated based off of TIA or stroke size. Subjects in the Warfarin arm will return to clinic with unscheduled INR checks until they reached the standard INR of 2.0 to 3.0.

Hypertension will be treated per the AHA/ASA guidelines and are described below:

Goals for target blood pressure level or reduction from pretreatment baseline are uncertain and should be individualized, but it is reasonable to achieve a systolic pressure less than 140 mm Hg and a diastolic pressure less than 90 mm Hg. For patients with a recent lacunar stroke, it might be reasonable to target a systolic blood pressure of less than 130 mm Hg.

Resumption of Blood Pressure therapy is indicated for previously treated patients with hypertension.

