## 5.6 Unscheduled Visits

### 5.6.1 Super-therapeutic/Sub-therapeutic INR

If the subject is not within therapeutic range they will be expected to return to clinic for an unscheduled visit to check the INR value until therapeutic range is met per the warfarin dosing protocol. These visits will be scheduled per PI discretion.

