**8.1.4 Potential Confounders**

Age and sex as well as a variety of clinical variables (e.g. CHADS2-VASc, CHA2DS2) that are risk factors for embolic stroke, and their associations with fatal or recurrent embolic stroke or hemorrhagic cerebral bleed will be examined. Other clinically relevant variables that are shown to differ between treatment regimens at enrollment will also be examined as potential confounders.

For missing data, both an intent-to-treat analysis (in which subjects are analyzed according to their randomized assignment) and a per-protocol analysis (in which subjects not treated according to their randomized assignment and/or with other major protocol violations are removed from this analysis) will be conducted. Sensitivity analyses to assess the effect of missing outcome data on the primary result will be conducted

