#### **11.2.1 Sources of Materials**

Data from study visits will be recorded on clinical research forms (CRF) and entered into a secure electronic database. All study records will be kept confidential and each subject will be assigned a unique study identification number which will be used on all research records. The identity of patients will only be known to site personnel and the PI. Original records will be kept in locked files at each site and copies of these records will be kept in a locked drawer in a secure office at the PI's site. Subject information will not be released without the subject's written consent except to the IRB, FDA and other regulatory monitoring bodies as necessary.

Data to be recorded for this study include CT/MRI confirmation of stroke; EKG, physical exams; vital signs; copies of baseline labs and EKG reports (if available within previous 6 months); medical history; concomitant medications; Records will be retained in secure storage for 7 years after the study concludes.

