### 11.4 Regulatory and Ethical Considerations

This study will be conducted in accordance with Good Clinical Practice (GCP), as defined by the International Conference on Harmonisation (ICH) and in accordance with the ethical principles underlying European Union Directive 2001/20/EC and the United States Code of Federal Regulations, Title 21, Part 50 (21CFR50).

The study will be conducted in compliance with the protocol. The protocol, any amendments, and the subject informed consent will receive Institutional Review Board/Independent Ethics Committee (IRB/IEC) approval/favorable opinion before initiation of the study.

All potential serious breaches must be reported to Bristol Myers Squibb (BMS) immediately. A serious breach is a breach of the conditions and principles of GCP in connection with the study or the protocol, which is likely to affect, to a significant degree, the safety or physical or mental integrity of the subjects of the study or the scientific value of the study.

Study personnel involved in conducting this study will be qualified by education, training, and experience to perform their respective tasks.

This study will not use the services of study personnel where sanctions have been invoked or where there has been scientific misconduct or fraud (eg, loss of medical licensure; debarment).

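### Stroke endpoints are adjudicated with patient and arm known; review from redacted files would reduce avoidable room for classification bias at that step

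*Combined protocol and SAP*

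**What the plan says.** Section 4.1 describes a "multi-center, open label, randomized, active control, parallel-group pilot trial". Section 2.3 sends every stroke endpoint to the Stroke Adjudication Committee and adds: "The committee will not be blinded to patient and study medication arm during the review of each stroke endpoint case". Section 2.1 makes the chair of the Executive Committee the third adjudicator when consensus is needed.

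Three other places might be taken for a safeguard, but none provides masked classification of events:

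- Sections 8.1.6 and 11.2 mention blinding, but only of the allocation scheme and the randomisation envelopes.
- Section 8.1.4 says "Sensitivity analyses to assess the effect of missing outcome data on the primary result will be conducted". That concerns outcomes that are absent, not outcomes put in the wrong class.
- Section 11.2.1 says "each subject will be assigned a unique study identification number which will be used on all research records". This offers a way to hide identity, but section 2.3 says that adjudicators know the patient.

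The supplied text gives no reason for unmasked review. Section 2.3.1 (Adjudicators) is not in the supplied text, so the make-up of the committee is not judged here.

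**The concern.** In an open-label trial, patients and sites know the treatment. The adjudicators need not, so adjudication is a step where masking is still possible, and the plan gives it up.

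The imaging definitions in section 2.3.2 and the scheduled scans in section 5.5 limit discretion. Three calls in the primary endpoint still need judgement:

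- **Whether a death is a fatal stroke.** Section 2.3.2 defines stroke types but, in the supplied text, gives no rule for attributing a death.
- **Whether a new deficit is a recurrent stroke or worsening of the index stroke.** This is an inference: section 7.5.1 only says that NIHSS tracks progression of the index event.
- **Whether an episode is a TIA.** This matters where TIA is in the composite, as in sections 3.2 and 8.1.2. Section 7.1 lists new haemorrhagic stroke instead.

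The confidence interval planned in section 8.1.2 reflects sampling error and would not show a classification bias. Section 8.1.5 says that the pilot is meant to inform larger studies, so any bias would carry into their planning.

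**Working it through.** The plan states no figure on this point, so there is none to reproduce. Three things can be checked.

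**1. What in a file would reveal the arm.** Section 1.3 has the control arm "receive standard of care warfarin starting at day 7±5 (TIA) or day 14 ±5 (small to medium ischemic stroke" days. Set against the apixaban windows in the same section:

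| Group | Apixaban start day | Warfarin start day | Shared days |
|---|---|---|---|
| TIA | 0–3 | 7±5 = 2–12 | 2 and 3 |
| Small stroke | 3–5 | 14±5 = 9–19 | none |
| Medium stroke | 7–9 | 14±5 = 9–19 | 9 |

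The start day therefore nearly identifies the arm. INR checks do too. Section 5.2 says "Subjects in the Warfarin arm will return to clinic with unscheduled INR checks", and section 5.6.1 says of a subject outside the therapeutic range that "they will be expected to return to clinic for an unscheduled visit to check the INR value".

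These visits cannot simply be deleted from the file. The Schedule of Study Procedures ticks physical examination, NIHSS and ECG for unscheduled visits as well as PT/INR. Deletion could strip neurological data from warfarin files only.

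**2. How far a few calls move the result (illustration, assumed counts).**

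Inputs:
- 120 subjects at 1:1 (section 4.1) give 60 per arm.
- Control risk of 20% (section 8.1.5) gives 60 × 0.20 = 12 events.
- The 5 apixaban events are an assumption: 60 × 0.20 / 2.30 = 5.2, where 2.30 is the first risk ratio tabulated in section 8.1.5.
- The second case, 12 v 12, assumes no difference.

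Method: risk difference = warfarin minus apixaban. The 95% CI is the difference ± 1.96 × √[p₁(1−p₁)/60 + p₂(1−p₂)/60]. The p-value is the Wald test in a two-arm logistic model. Two arms stand in for the six-level model of section 8.1.2 because subgroup event counts are not given.

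For 12 v 5: 0.200 − 0.083 = 0.117. Half-width = 1.96 × √(0.002667 + 0.001273) = 0.123.

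| Warfarin v apixaban events | Risk difference, points (95% CI) | p |
|---|---|---|
| 12 v 5 | 11.7 (−0.6 to 24.0) | 0.075 |
| 13 v 4 | 15.0 (2.8 to 27.2) | 0.025 |
| 11 v 6 | 8.3 (−4.1 to 20.7) | 0.197 |
| 12 v 12 | 0.0 (−14.3 to 14.3) | 1.00 |
| 13 v 11 | 3.3 (−11.0 to 17.6) | 0.65 |
| 11 v 13 | −3.3 (−17.6 to 11.0) | 0.65 |

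One call changed in each arm, in opposite directions, moves the difference by 2/60 = 3.3 points. Two calls changed in the same direction (12 v 5 to 13 v 6) would leave it at 11.7.

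At 50 per arm, the group size in section 8.1.5, the shift is 2/50 = 4.0 points. An assumed 10 v 4 goes from p = 0.094 to 0.030 (11 v 3) or 0.255 (9 v 5).

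**3. Workload.** Fatal or recurrent stroke files range from 12 + 5 = 17 to 15 + 15 = 30. The 15 is 25% of 60, the risk in section 1.2. TIA, asymptomatic haemorrhage and referred non-events come on top, and their number is not given. No firm upper limit follows: section 4.2.2 allows up to 125 randomised, and one patient can be referred more than once.

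**The case against.** The strongest reply is that this is an openly stated choice in a small open-label pilot, and that masking may achieve little. If the adjudicators treat patients at the four sites, they may recognise cases anyway. Section 2.3.1 is not available to settle that. The third member may also learn arm-level information: section 2.2 sends DSMB recommendations to the Executive Committee, and the trial-wide suspension rule in section 7.5.2 counts symptomatic haemorrhagic events in the apixaban arm. Frequent unscheduled visits could hint at warfarin even with the reason removed.

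These points stand as limits on how well masking will work, and the fix allows for them. They do not give a reason to show adjudicators the arm.

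It is also fair to say that the 12 v 5 illustration starts close to the 0.05 threshold. Its 5 comes from a power table that does not reproduce with 20% as the control risk: a ratio of 2.30 at 50 per group gives about 36% power, not 80%. The illustration therefore shows fragility at one set of counts and does not measure bias.

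A reader might go further and infer that the trial's result will be biased towards apixaban, or that crossing 0.05 at 12 v 5 shows the conclusion to rest with the adjudicators. The documents support neither. They give no misclassification rate, the bias could run either way, and at 12 v 12 the same shift changes nothing.

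**Conclusion.** The concern holds as a risk of bias that the plan could reduce and does not. Section 2.3 is explicit, no supplied section offsets it, and open-label treatment does not require it. The size and direction of any bias cannot be derived from the documents.

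Under the assumed counts, a 3.3-point shift compares with a half-width of about 12 points (12 v 5) to 14 points (12 v 12), so sampling error is larger than the shift. The change is worth making because it is cheap and because the pilot feeds later planning. Unmasked review does not by itself invalidate the primary result. Nor do the documents support a claim that the committee is conflicted, since its membership is not in the supplied text.

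**What to change.** In section 2.3, replace the sentence on blinding with:

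> Post-randomisation endpoint cases are adjudicated by the committee, including the third member when called, from files identified by study number only, with patient identifiers, treatment arm, anticoagulant names, INR values, the reason for unscheduled visits, and study-drug dosing and start dates removed; neurological examination, NIHSS and imaging data from all visits, including unscheduled ones, are kept.

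State also that:

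- existing study staff who take no part in adjudication do the redaction;
- the third member adjudicates before seeing any arm-level outcome data and, where that is not possible, those cases are reported as unmasked.

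The size grouping before randomisation (section 6.2) and DSMB reporting (section 2.2) stay as they are.

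**Cost.** One amendment at a four-site trial. Section 11.4 says: "The protocol, any amendments, and the subject informed consent will receive Institutional Review Board/Independent Ethics Committee (IRB/IEC) approval/favorable opinion". Add redaction time for roughly 17 to 30 fatal or recurrent stroke files at the assumed risks, plus an unknown number of TIA, asymptomatic haemorrhage and non-event referrals. The documents do not say who would redact, so the staff time is an assumption. Masking will be imperfect, and bias in which events unblinded sites detect and refer remains.

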### 2.3.2 Stroke/TIA Subtype Classification

#### 2.3.2.1 Ischemic Stroke

Defined as an acute symptomatic focal cerebral or retinal dysfunction caused by an infarction of central nervous system tissue.

1. a. Acute infarcts are classified as small, medium or large based on size of the largest ischemic lesion:
  - a. small = lesion in the anterior or posterior circulation <1.5 cm.
  - b. medium = equal to or greater than 1.5cm but less than a complete territory infarct lesion in a cortical superficial branch of the anterior cerebral artery (ACA), middle cerebral artery (MCA), posterior cerebral artery (PCA), or in a branch of MCA or PCA, or lesion in internal border-zone territories.
  - c. large posterior = lesion involving complete PCA territory, or lesion of cerebellum 1.5 cm or larger or any lesion of the brain stem.

- d. large anterior = lesion involving complete ACA or MCA territory, or lesion involving >1 artery territory
  - e. All classifications are based of the measurement of the largest lesion size with preferred sequencing to be GRE on MRI (*but all effort should be used to maintain the same modality of sequencing and magnet strength used at baseline*)
- 2.Subacute/chronic or 'old' infarcts (i.e. more than 2 weeks) are noted but not classified.
- 3.Transient Ischemic Attack (TIA)  
defined as an acute symptomatic focal cerebral, spinal, or retinal dysfunction in which symptoms resolve (typically in less than 1 day) without acute damage on neuroimaging.

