### **2.3.2.2 Hemorrhagic Stroke**

Defined as an acute symptomatic focal or global cerebral dysfunction caused by a nontraumatic intraparenchymal, intraventricular, or subarachnoid hemorrhage; or asymptomatic neuroimaging-positivity, including greater than three cerebral microbleeds found with GRE-sequencing and/or CT hyperintensities

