#### 4.3.2 Exclusion Criteria

1. Hemorrhagic stroke
2. Large ischemic stroke
3. History of major bleeding within the last 6 months from time of subject enrollment (e.g. GI bleed).
4. History of intracranial bleed
  - a. Traumatic intracranial bleed within one year of randomization. (Traumatic ICH greater than one year of randomization is not an exclusion).
5. Current or history of bleeding disorders (e.g. blood dyscrasias)
6. Blood Pressure of 180/100 mmHg on hypertensive therapy day of randomization per PI discretion.
7. Current illicit drug use and/or chronic alcohol use per PI discretion.
8. Severe liver disease (AST/ALT 2x upper limit).
9. Patients with kidney disease meeting criteria to take 2.5 mg twice daily who are taking strong dual inhibitors of CYP3A4 and P-glycoprotein (e.g. ketoconazole, itraconazole, ritonavir, clarithromycin) .
10. Any other suspected etiology for stroke (e.g. ipsilateral carotid disease).
11. Greater than 3 Cerebral Micro-bleeds (CMB) on gradient recovery echo (GRE) or evidence of intracranial hemorrhage on CT at time of randomization. (SWI sequencing may be used if GRE sequencing is not obtainable)
12. Therapeutically anti-coagulated at time of admission (INR at admission greater than 2.0 on warfarin or took two consecutive doses of NOAC).
13. Absolute indication for use of warfarin only.( e.g. Mechanical Valve)
14. Absolute indication for anticoagulation prior to randomization window. (e.g. DVT)
15. Hemoglobin less than 9 gm/dl and/or platelet count less than 100 K/uL.
16. Requires dual antiplatelet therapy.

17. Daily use of NSAIDS
18. Pregnancy or lactation.
19. Any use of an investigational product within the past 30 days.
20. Prisoners or subjects who are involuntarily incarcerated.
21. Subjects who are compulsorily detained for treatment of either a psychiatric or physical (eg, infectious disease) illness.
22. Concurrent participation in another clinical study where use of an investigational product is used

Subjects that do not meet all of the enrollment criteria may not be enrolled. Any violations of these criteria will be reported in accordance with IRB Policies and Procedures.

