## 7.5 Efficacy and Safety Evaluations (see also schedule of events)

### 7.5.1 Diagnostic Tests, Scales, Measures, etc.

*MRI w/o contrast (GRE sequencing preferred but all effort should be used to maintain the same modality of sequencing and magnet strength from baseline or CT w/o contrast –*

Will be performed, along with the NIHSS, to measure the size of ischemic stroke at screening. It will also be used for follow-up assessments to indicate any early hemorrhagic transformation or micro-embolic strokes. Patients who are unable to have a MRI due to contraindication (i.e. implantable pacemaker) will have be allowed to use CT with the NIHSS.

- TIA- will have no ischemic changes
- Acute infarcts are classified as small, medium or large based on size of the largest ischemic lesion:
  - small = lesion in the anterior or posterior circulation <1.5 cm.
  - medium = equal to or greater than 1.5cm but less than a complete territory infarct lesion in a cortical superficial branch of the anterior cerebral artery (ACA), middle cerebral artery (MCA), posterior cerebral artery (PCA), or in a branch of MCA or PCA, or lesion in internal border-zone territories.
  - large posterior = lesion involving complete PCA territory, or lesion of cerebellum 1.5 cm or larger or any lesion of the brain stem.
  - large anterior = lesion involving complete ACA or MCA territory, or lesion involving >1 artery territory
- All classifications are based of the measurement of the largest lesion size.

*TEE-*

Will be obtained or scheduled prior to discharge on all patients or will be scheduled as part of their evaluation for potential cardiac sources of emboli. In addition to imaging specifically of left atrium thrombus; measurements will be obtained for left atrial size, left atrium appendage, velocity, left ventricle size and function and other significant myocardial or valvular heart disease.

*Carotid ultrasound-*

Will be performed on all patients to rule out ipsilateral carotid disease during the screening visit.

*Laboratory evaluations-*

Will be obtained from all patients at screening, day 30, day 90 and day 180. Additional lab measurements for the warfarin group will be obtained monthly and at unscheduled visits if warranted by the warfarin dosing protocol.

*Event Monitor-*

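### The plan prefers GRE, its blood-detection sequence, for measuring infarcts and names no sequence suited to acute infarction, so strata, start windows and some event classifications rest on a poorly specified read.

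*Combined protocol and SAP*

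**What the plan says.** On sizing the infarct, section 2.3.2.1, item 1e, reads "All classifications are based of the measurement of the largest lesion size with preferred sequencing to be GRE on MRI". Section 7.5.1 describes the same non-contrast scan with "GRE sequencing preferred but all effort should be used to maintain the same modality of sequencing and magnet strength from baseline". It says the scan "Will be performed, along with the NIHSS, to measure the size of ischemic stroke at screening", and of follow-up: "It will also be used for follow-up assessments to indicate any early hemorrhagic transformation or micro-embolic strokes".

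On finding blood, the hemorrhagic stroke definition (2.3.2.2) includes "greater than three cerebral microbleeds found with GRE-sequencing". Exclusion criterion 11 (4.3.2) also counts microbleeds on GRE and allows SWI as a substitute. SWI is the only other MRI sequence named. No diffusion-weighted, FLAIR or other infarct sequence appears.

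On TIA, section 2.3.2.1 requires symptoms that resolve "without acute damage on neuroimaging". Section 7.5.1 gives an imaging condition only: "TIA- will have no ischemic changes". Neither names a sequence.

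The resulting class (TIA, small, medium or large) is used in four places:
- the randomization stratum (5.2, 8.1.6);
- the start window (5.2, 5.3 and Table 2);
- the exclusion of large stroke (4.3.2), where 2.3.2.1 counts any brain stem lesion as large;
- the six-level SUBGROUP factor in the logistic model (8.1.2).

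**The concern.** GRE serves two different purposes here: counting blood products and measuring a fresh ischemic lesion. It is the only sequence named for the second. Section 5.2 places baseline and randomization within 48 hours of symptoms, when the boundary between TIA and small stroke depends heavily on what the sequence can show. If it shows early small infarcts poorly, three errors are possible at baseline:
- a patient whose symptoms resolve, with a small infarct that was not seen, is classed as TIA;
- a lesion is under-measured and falls below 1.5 cm;
- a brain stem lesion is not seen, and a patient whom the protocol excludes is enrolled.

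The instruction to keep the baseline sequence carries the same preference into follow-up scans that are meant to reveal new small emboli. For recurrent events, the same reading decides between ischemic stroke and TIA. Section 7.1 omits TIA from the primary composite, while 3.2 and 8.1.2 include it. Under 7.1 a transient event with an unseen infarct would therefore not count; under 8.1.2 it would count either way.

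**Working it through.** The plan states no figure on this point, so there is none to reproduce. The check covers the text, the start windows and the planned stratum size.

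**1. Which sequence serves which purpose.**

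| Purpose | Sequence named | Where |
|---|---|---|
| Size of largest ischemic lesion | GRE, preferred | 2.3.2.1 item 1e; 7.5.1 |
| Microbleed count, eligibility | GRE, or SWI if GRE is not obtainable | 4.3.2, criterion 11 |
| Microbleeds, outcome | GRE | 2.3.2.2 |
| Presence or absence of acute infarct (TIA) | none | 2.3.2.1 item 3; 7.5.1 |

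**2. What a wrong class does to the assigned start.** Windows are from Table 2.
- Small stroke classed as TIA, apixaban: days 3-5 become days 0-3. The windows share day 3 only. The largest shift is 5 − 0 = 5 days; the smallest is none.
- Small stroke classed as TIA, warfarin: 14±5 is days 9-19 and 7±5 is days 2-12. The windows share days 9-12. The largest shift is 19 − 2 = 17 days; the smallest is none.
- Medium stroke classed as small, apixaban: days 7-9 become days 3-5, with no shared day. The shift is 7 − 5 = 2 to 9 − 3 = 6 days.
- Medium stroke classed as small, warfarin: same window, no shift.

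**3. How many patients.** Section 8.1.6 gives four blocks of 10 per stroke type: 4 × 10 = 40 per stratum, 3 × 40 = 120 in all, and 40 / 2 = 20 per arm. The documents give no miss rate. For an assumed share m of 40 patients with small infarcts classed as TIA, the expected number is 40m, of whom 20m are on apixaban. The chance of at least one on apixaban is 1 − (1 − m)^20:

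| Assumed m | Of 40 | Of 20 on apixaban | Chance of at least one on apixaban |
|---|---|---|---|
| 5% | 2 | 1 | 64% |
| 10% | 4 | 2 | 88% |
| 20% | 8 | 4 | 99% |
| 30% | 12 | 6 | >99% |
| 50% | 20 | 10 | about 100% |

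These rows illustrate scale and are not estimates. Each 10% is 4 patients.

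**4. Effect on the comparisons.** The class is assigned before 1:1 randomization within strata, so baseline errors should fall equally on both arms in expectation. The pooled apixaban-versus-warfarin contrast still compares randomized groups. The subgroup contrasts in 8.1.2 do not have this protection as descriptions of the named groups: with 20 patients per cell, 2 misplaced patients are 10% of a cell.

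**5. Follow-up scans.** Section 5.5 schedules imaging at day 14 and end of study, nominally 180 − 14 = 166 days apart. An infarct first seen at day 180 may be months old, and 2.3.2.1 treats infarcts of more than 2 weeks as old. A sequence chosen only for acute infarction would not be enough for that scan.

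**The case against.** The strongest reply is that the text does not require what is feared. GRE is preferred, not mandatory. Item 1e concerns how a lesion is measured, while the TIA definitions refer to imaging in general. An infarct seen on any other acquired sequence, or on CT, already rules out TIA. Section 6.1 has staff review the MRI results without limiting them to GRE. In addition, 2.3.2.1 requires symptoms to resolve, 7.5.1 uses the NIHSS alongside imaging, and 6.2 has the group confirmed from the adjudication committee's recommendation before randomization. The reference to baseline in item 1e suggests that the sentence was meant to keep follow-up scans comparable.

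Much of this stands. A reader might infer that every infarct invisible on GRE becomes a TIA by rule; the documents do not say so. A reader might also put the share missed at, say, 10 to 40% (4 to 16 of 40) and count all of them as starting in the wrong window. Nothing in the documents supports a rate, and the TIA and small-stroke windows partly overlap, so some would still start inside the correct one. Nor do the documents support a claim that the overall treatment comparison is biased by this alone.

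The safeguards do not settle the point, however. Neither the NIHSS nor the committee step says which sequence is to be read. The only written preference for sizing is the blood sequence. If sites read another sequence in practice, they may do so differently across four centers, with no instruction to record which was used. A drafting slip in this place still needs correcting.

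**Conclusion.** The preference for GRE in 2.3.2.1 item 1e and 7.5.1 points readers to the wrong kind of sequence for an assessment that sets the stratum, the assigned start window and eligibility, and that helps classify recurrent events. It should be changed.

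The size is unknown: 4 patients per 10% of a planned stratum of 40, with no miss rate in the documents. The conclusion rests on two assumptions. One is that GRE shows small infarcts poorly in the first 48 hours, which is general imaging knowledge. The other is that readers follow the stated preference. Exposure to the TIA error is limited to patients whose symptoms resolve under 2.3.2.1, and is wider under the imaging-only wording of 7.5.1. What is at risk is the meaning of the strata and six-subgroup contrasts, adherence to the protocol's own timing rule, the large-stroke exclusion, and the split of recurrent events into ischemic stroke and TIA.

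**What to change.** In 2.3.2.1 item 1e and in 7.5.1, separate the two purposes and use the same wording in both:
- Presence and size of acute infarction, at baseline and at suspected events, are read on DWI from the same non-contrast MRI session. CT remains the fallback where MRI is contraindicated, as 5.5 and 7.5.1 already provide.
- GRE or SWI is used for hemorrhage and microbleeds. The instruction to hold sequence and magnet strength constant applies to that comparison.
- Day-14 and end-of-study scans also name a sequence that shows non-acute infarcts, such as T2 or FLAIR, to find lesions that are new since baseline.
- The sequence used for each read is recorded as a data field.

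The two TIA wordings should be aligned in the same amendment. The cost is amendment text, reader instructions and one data field, with no extra visit. The downside is that some patients will move from the TIA to the small-stroke stratum. No change to the start windows is proposed.
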